4 DEFINITION OF TERMS

Assessment	A procedure used to generate data required by the study.
Accelerated Phase (AP)	
• $\geq 15\%$ blasts in the peripheral blood or bone marrow aspirate, but $< 30\%$ blasts in both the peripheral blood and bone marrow aspirate;• $\geq 30\%$ blasts plus promyelocytes in peripheral blood or bone marrow aspirate;• $\geq 20\%$ basophils in the peripheral blood;• Thrombocytopenia ($<100 \times 10^9/L$) that is unrelated to therapy.
Blast Crisis (BC)	$\geq 30\%$ blasts in peripheral blood or bone marrow aspirate Appearance of extra medullary involvement other than hepatosplenomegaly proven by biopsy (i.e., chloroma).
Complete Hematologic Response (CHR)	
• Complete normalization of peripheral blood counts with leukocyte count $<10 \times 10^9/L$• Platelet count $<450 \times 10^9/L$• No immature cells, such as myelocytes, promyelocytes, or blasts in peripheral blood• No signs and symptoms of disease with disappearance of palpable splenomegaly
Complete Molecular Response (CMR)	Undetectable BCR-ABL levels with high sample sensitivity (10^{-5} or greater) for a minimum of 2 years.
Cytogenetic Response (CyR)	
• Complete (CCyR): 0% Ph+ metaphases.• Partial (PCyR): > 0 to 35% Ph+ metaphases.• Minor (mCyR): >35 to 65% Ph+ metaphases.• Minimal: >65 to 95% Ph+ metaphases.• None: > 95 to 100% Ph+ metaphases.
Cycle of treatment	28 days of treatment
Disease Progression	The following events are considered disease progression: 
• AP.• BC.• CML-related death.
Enrollment	It is the time until all patients are included in the study, i.e. all patients received at least one dose of study medication. Previously they must have signed an informed consent (i.e., prior to starting any of the procedures described in the protocol).
Full Analysis Set (FAS)	The full analysis set (FAS) comprises all patients who complete the treatment with bosutinib in combination with atezolizumab for 12 cycles successfully.

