Medicinal product for Human Use or Investigational Drug	Any substance or combination of substances presented as having properties for treating or preventing disease in human beings or which may be used in or administered to human beings either with a view to restoring, correcting or modifying physiological functions by exerting a pharmacological, immunological or metabolic action, or to making a medical diagnosis (Royal Decree 1090/2015, of 4 December).
Loss of Complete Hematologic Response	Loss of CHR is defined as the appearance of any of the following, confirmed by a second determination ≥ 4 weeks later (unless associated with progression to AP/BC or CML-related death): 
• WBC count that rises to $> 20.0 \times 10^9/L$;• Platelet count that rises to $\geq 600 \times 10^9/L$;

	
• Progressing hepatosplenomegaly to a size \geq 5 cm below the left intercostal margin;• Appearance of \geq 5% myelocytes + metamyelocytes in the peripheral blood;• Appearance of blasts or promyelocytes in the peripheral blood.
Molecular Response (MR)	
• MMR – BCR-ABL \leq 0.1% (IS).• MR4 – BCR-ABL \leq 0.01% (IS).• MR4.5 \leq 0.0032% (IS).• UNDETECTABLE.
Overall Survival (OS)	OS is calculated from the first day of therapy to the date of death. Surviving patients will be censored at the time of the last follow-up.
Subject Number	A unique identifying number assigned to each patient who enrolls (i.e. signs the IC) in the study.
Per-Protocol Set (PPS)	A subset of the full analysis set (FAS) who is compliant with the clinical study protocol (i.e. Composed by subjects that have not incurred in major protocol deviations that could jeopardize the validity of the data and the study outcomes).
Premature Patient Withdrawal	When a subject exits from the study prior to the planned completion of all study treatment administration and/or assessments or procedures. From this time, all study treatment administration is discontinued and no further assessments or procedures will be done, other than the monitoring for progression and/or survival.

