Progression Free Survival (PFS)	Progression free survival (PFS) is defined as the time from the date of first treatment administration until the time of disease progression. Subjects who die without a reported progression will be considered to have progressed on the date of their death. Subjects who do not progress nor die will be censored on the date of their last hematological assessment.
Safety Set (SS)	Composed by all subjects who received at least one dose of study medication.
Study Treatment	Includes any drug or combination of drugs in any study arm administered to the subject as part of the required study procedures.
Trial Subject	An individual who participates in a clinical trial, either as recipient of an investigational medicinal product or as a control.
Variable	Identifier used in the data analysis; derived directly or indirectly from data collected using specified assessments at specified time points.

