12.12 Physical Examination and Extra-medullary Leukemia Involvement

A complete physical examination will include the examination of general appearance, skin, neck (including thyroid), eyes, ears, nose, throat, lungs, heart, abdomen, back, lymph nodes, extremities, vascular, and neurological. Presence of extra-medullary leukemic involvement will be checked along with each physical examination as outlined above. Findings on physical examination consistent with extra-medullary leukemic involvement will be recorded (e.g., lymph nodes, liver and spleen size). With regards to lymph nodes, only those palpable lymph nodes should be considered to be CML related if leukemic blast infiltration has been confirmed via biopsy/histology or by technically adequate (not contaminated with peripheral blood) aspiration cytology. When extra-medullary involvement other than the spleen or liver is the only evidence of blast crisis, this finding must be confirmed by technically adequate (not contaminated with peripheral blood) aspiration cytology and /or biopsy (especially for isolated lymph nodes) and data entered into the extra-medullary involvement eCRF.

Information about the physical examination must be present in the source documentation at the study center and will be collected during the following visits:

- Screening
- During first therapy:
 - Day 1 of cycle 1 (before treatment).
 - Day 15 of cycle 1.
- During second therapy (before treatment):
 - Day 1 of cycle 2. Before the patient takes the bosutinib plus atezolizumab combination for first time.
 - Day 1 of cycles 4, 7, 10, and 13.
- During third therapy:
 - Day 1 of cycle 14. Before the patient takes bosutinib 400 mg/day in monotherapy, for the first time again for the treatment of CML.
 - Day 1 of cycles 17, 20 and 23.
 - At the End of Treatment: Day 29 (Last dose) of cycle 25.
 - At the End of Study, (visit EOS or follow up): 28 days after the last dose.

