12.20 End of Treatment or Early Termination Procedures

The end of treatment for the early termination visit should be performed within 2 weeks (14 days) of the patient's last dose of study drug or the patient/investigator decision to discontinue treatment. Survival information, stem cell transplantation, TKI therapy status, as well as information on the status of the patient's disease (i.e., disease progression to AP/BC according to protocol definition, or CML related death) will be collected, if applicable. The information may be collected from tests that were performed for the study or as part of the patient's routine medical care.

Patients that finished the study as per protocol will continue to receive treatment for CML, according to standard clinical practice. For those patients who withdraw before the end of the study, their physician will decide the best course of treatment indicated, following the standard clinical practice and current guidelines for the treatment of CML.

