6.5. Analysis methods

Descriptive statistics are presented using mean and standard deviations for continuous variables and count and percentages for categorical variables. The 95% confidence interval (CI) for a proportion will be reported for the primary efficacy variable. The Shapiro-Wilks test will be used to test the normality of the distribution of continuous variables. Statistical differences between groups were analyzed using the chi-square test for categorical data and the Student's t test for quantitative data. Quantitative data showing non-normal distribution were analyzed using the Mann-Whitney U test. The Kaplan-Meier method is used to study survival. A p-value of <0.05 was considered statistically significant. All analyses were carried out with the free statistical program R (<https://cran.r-project.org/>).

Primary Objective:

Frequency and percentage of adverse events will be summarized by system organ class and/or preferred term, severity (based on CTCAE grades), type of adverse event and causality relation to study treatment by the study phases. 95% confidence intervals of the proportion of adverse events will be computed using the exact binomial distribution.

Secondary Objectives: The rates of molecular responses at certain time points as well as the percentages will be presented together with an exact 95% binomial confidence interval.

All time to event endpoints will be analyzed using the Kaplan-Meier method and will be presented by Kaplan-Meier method plots.

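### The PFS rule keeps events learned of after withdrawal but can drop event-free time after withdrawal, so Kaplan-Meier censoring can depend on outcome; the net direction depends on an analysis set the plan does not name

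*Protocol*

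**What the plan says.** **Events.** Protocol Section 4 measures PFS from first treatment to disease progression (accelerated phase, blast crisis or CML-related death). It adds: "Subjects who die without a reported progression will be considered to have progressed on the date of their death". No event is excluded because it follows withdrawal.

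**Censoring.** For all other patients: "Subjects who do not progress nor die will be censored on the date of their last hematological assessment". Overall survival, in the same section, works differently: "Surviving patients will be censored at the time of the last follow-up".

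**After withdrawal.** The definition of premature withdrawal says that "no further assessments or procedures will be done, other than the monitoring for progression and/or survival". Section 12.20 collects survival and disease status at early termination: "The information may be collected from tests that were performed for the study", or from routine care. No schedule is given for later monitoring, and nothing says whether a routine-care blood count is a hematological assessment for PFS.

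**Analysis.** SAP 6.5 states: "All time to event endpoints will be analyzed using the Kaplan-Meier method". It gives no PFS censoring rule. SAP 6.6 describes carrying observations forward and backward for time-to-event endpoints, which does not settle the censoring date.

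**Analysis set.** None is named for PFS. Protocol 11.6 links the efficacy analysis to the per-protocol set. That is a subset of the full analysis set (FAS), which holds only patients who completed the combination phase.

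**Event definition.** For extramedullary blast crisis, Section 4 has "Appearance of extra medullary involvement other than hepatosplenomegaly proven by biopsy (i.e., chloroma". Section 12.12, where such involvement is the only evidence of blast crisis, has "this finding must be confirmed by technically adequate (not contaminated with peripheral blood) aspiration cytology and /or biopsy".

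**The concern.** Take two patients withdrawn on the same day and monitored equally long, with no further blood assessment. One dies at month 18 and stays in the risk set until then. The other is documented alive and progression-free at month 18, yet leaves the risk set at the last blood assessment, around withdrawal. Their censoring is decided by their later outcome, which Kaplan-Meier does not allow for. Each late event is divided by a risk set that has lost comparable event-free patients, so the curve falls too far at that event.

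The protocol has several routes to compulsory withdrawal: bosutinib compliance below 70%, four or more missed atezolizumab administrations, and a bosutinib interruption longer than one month. In a disease with few progressions or deaths, one or two late events shape the whole curve.

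**Working it through.** **The plan's only attrition figure.** Protocol 15.5 and SAP 4.3 assume that at most 15% of 36 patients will not go on to the combination: 36 × (1 − 0.15) = 30.6, which reproduces the stated 30-31. The plan gives no attrition for later cycles and no expected PFS, so every size below rests on assumptions.

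**Worked example (assumed data, n = 36).** 24 patients complete and are censored event-free at day 728. Six withdraw at day 29, one of whom dies on day 500. Six withdraw at day 365, one of whom dies on day 600. No blood assessment follows withdrawal. Kaplan-Meier PFS at day 700 is the product of (1 − events / number at risk).

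| Rule | Day 500 | Day 600 | PFS |
|---|---|---|---|
| As written | 25/26 | 24/25 | 24/26 = 92.3% |
| Other withdrawn patients documented progression-free to day 728 | 35/36 | 34/35 | 34/36 = 94.4% |
| Events and time both stop at withdrawal | no event | no event | 100% |

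In the first row the 10 event-free withdrawn patients have left the risk set before day 500, leaving 24 + 2 = 26. Overall survival in the same patients, censored at last follow-up, is also 34/36 = 94.4%. Every PFS event here is a death, so the 2.1-point gap between PFS and overall survival comes from the censoring rule alone.

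Restricted to the 30 patients who reached day 365, only the day-600 death counts: 24/25 = 96.0% as written, against 29/30 = 96.7%.

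**Large-sample simulation.** 400,000 patients per scenario, with blood counts on the days in Protocol 12.15.1. Assumptions not in the documents:
- day-700 PFS without withdrawal of 90 to 97%;
- 15% withdrawn at day 29, plus 0, 15 or 30% spread over days 29 to 700;
- hazard after withdrawal unchanged or tripled;
- complete capture of events to day 728;
- no qualifying blood count after withdrawal.

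The 95.7% scenario borrows the 4.3% progression figure that Protocol 6.2 gives for previously treated chronic-phase patients. It only sets a range.

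| Withdrawn | Unchanged hazard: true → as written | Tripled hazard: true → as written |
|---|---|---|
| 15% | 95.7 → 95.0 | 94.5 → 93.7 |
| 30% | 95.7 → 94.4 | 93.9 → 92.3 |
| 45% | 95.7 → 93.8 | 93.4 → 90.6 |

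The shift is about −0.7 to −1.9 points with unchanged hazard and −0.8 to −2.8 with tripled hazard. Across all assumed scenarios with withdrawal it runs from −0.5 (97.0 → 96.5) to −5.2 (84.9 → 79.8). Without withdrawal it is zero. Censoring at the last date known event-free recovers the true value each time.

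**Completers only.** Keeping patients still on study and event-free beyond day 365, as a stand-in for the FAS, the rule's own effect is 0 to −0.9 points (94.1 → 93.2 at the extreme). The resulting estimate nevertheless lies 1.3 points (98.3 against 97.0) to 8.3 points (93.2 against 85.0) above all-patient PFS, because a patient must stay event-free for about a year to enter the set while PFS time starts at first treatment.

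**The case against.** Three objections carry weight.

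**Analysis set.** The only set tied to efficacy is the per-protocol set. If PFS follows it, patients withdrawn before the end of the combination add neither events nor time, and only third-therapy withdrawals matter. A reader might infer that the reported PFS is biased low overall. The documents do not support that: in completers, the upward selection is larger than the downward effect of the rule. This stands, although an opposite bias does not repair outcome-dependent censoring.

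**Blood counts after withdrawal.** Monitoring for progression is exempt from the stop on assessments, accelerated phase and blast crisis are defined largely by blood or marrow findings, and routine-care tests may be used. If such counts qualify as hematological assessments, event-free patients gain a later censoring date and the asymmetry for progression shrinks or disappears. This also stands. What remains firm is deaths found by survival-only contact.

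**Size and capture.** Withdrawal beyond the 15% has no source in the plan, and no later monitoring schedule is given, so late events may not be captured. The listed endpoint is a number of progression-free patients at end of treatment; the censoring date affects the Kaplan-Meier estimate, not a simple count. PFS is a descriptive secondary endpoint in a small exploratory study: two events in 36 patients (34/36) carry an exact 95% interval of 81.3 to 99.3%, much wider than the effect.

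Two other stronger readings also fail. Withdrawn patients do not contribute events without any follow-up time: time up to the last assessment is counted, and only later event-free time is lost. Nor is it a fault in itself that PFS and overall survival use different censoring dates, since a survival contact shows that a patient is alive, not progression-free.

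**Conclusion.** The concern holds in limited form. As written, the PFS definition lets censoring depend on outcome wherever monitoring after withdrawal yields no qualifying blood assessment, and nothing in the SAP corrects it. By itself the rule lowers Kaplan-Meier PFS by about 0.5 to 5 points in all treated patients and by about 0 to 0.9 points in completers. Both ranges rest on the assumed event rates, withdrawal rates and event capture set out above. The net direction of bias in the reported figure cannot be stated until the analysis set is named.

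The biopsy-versus-cytology conflict is real but separate. A patient whose only evidence of blast crisis is cytology-proven extramedullary disease is a PFS event under Section 12.12 and not under Section 4. It contributes nothing to the sizes given here.

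**What to change.** 1. In Protocol Section 4 and SAP 6.5, censor event-free patients at the last date documented alive and progression-free, from any source that could also have supplied an event: study tests, routine-care tests or post-withdrawal monitoring. Say which assessments qualify. A survival-only contact does not by itself document freedom from progression, so record progression status at each contact where possible.
2. Add a sensitivity analysis that stops both events and time at withdrawal, or at the last hematological assessment. It covers patients followed for survival only. It should not be the main analysis: in the simulation it recovers PFS when hazard is unchanged after withdrawal, but with tripled hazard it reads too high (95.7% against 93.4% with 45% withdrawn).
3. Name all treated patients as the PFS analysis set.
4. Describe the post-withdrawal monitoring: which contacts, how often and until when.
5. Separately, reconcile Sections 4 and 12.12 to one standard of proof for extramedullary blast crisis as a PFS event.

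The cost is mainly protocol and SAP wording. Monitoring after withdrawal is already foreseen, but its schedule is not written, so item 4 and a dated progression-status field may add a little data collection.

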5 PROTOCOL SYNOPSIS

Sponsor	Fundación Española para la Curación de la Leucemia Mieloide Crónica (Fundación Zero LMC) [name] [name] Spain [contact]
Study Treatment	Bosutinib and Atezolizumab
Study Title	Multicenter, Open-Label, Phase Ib/II Clinical Trial to Evaluate Safety and Efficacy for the Combination of Bosutinib plus Atezolizumab in newly diagnosed Chronic Myeloid Leukemia Patients
Phase	Phase Ib/II
Eligible Population	Naïve patients with chronic-phase Chronic Myeloid Leukemia (CP-CML)
Summary and Study Rationale	
Since the introduction of imatinib and subsequent second-generation tyrosine kinase inhibitors (2GTKIs), the prognosis of chronic-phase Chronic Myeloid Leukemia (CP-CML) has improved greatly. Initially considered a lethal disease with a median estimated overall survival (OS) of 3.2 years, CP-CML is now regarded as a chronic disease with a life expectancy similar to that of the healthy population. However, Chronic Myeloid Leukemia (CML) patients, despite their treatment response, cannot be considered cured and must take the treatment indefinitely.
 
Recently, data from different clinical trials have shown how a minority of patients who achieve and maintain a deep molecular response with imatinib, could discontinue the treatment safely. Therefore, treatment free remission (TFR) has been established as a new goal for CML patients. However, at this moment, TFR is only available for a small group of patients, since deep molecular response is achieved in 5 years only in approximately 20% of patients treated with imatinib, and, unfortunately, 50% of patients will eventually relapse. In addition, recent data have shown how a time exposure to imatinib longer than 7 years can be a prognostic factor for TFR. Starting treatment with 2GTKIs (dasatinib, nilotinib and bosutinib) has demonstrated higher probabilities of deep molecular responses.
 
Suppression of the immune system in CML patients at diagnosis is mediated in part by hematopoietic stem cells, which acquire a proliferative/survival advantage and lose the ability to undergo apoptosis. Release of tumor-derived cytokines/chemokines drives the expansion of immune suppressor MDSC and Treg, facilitating downregulation of antitumor effector immunity. PD-L1 is upregulated on CML cells, where it interacts with the co-inhibitory receptor PD-1, and contributes to protection of the malignant cells from immune destruction. MDSC originate from the malignant BCR-ABL1 clone and mediate their suppressive activity via a number of mechanisms, including increased production of reactive oxygen and nitrogen species (NO, ROS), arginase-1, and TGF-β1. MDSC can induce Treg expansion, and Treg also express PD-1 to promote enhanced suppressor function. We know how PD-1 is expressed on T cells at diagnosis in CML patients, and that its expression decreases considerably after achieving deep molecular response. The combination of TKI plus interferon has resulted into higher probabilities of deep molecular responses compare to TKI monotherapy in several clinical trials.
 
It is also known how the immune system plays a crucial role in treatment free remission strategies. The lack of overt relapse in patients who have previously achieved a deep molecular response, despite the presence of very low levels of residual disease has been attributed to immunological control of CML. IFN/imatinib induction treatment followed by a temporary IFN maintenance may enable a higher rate of treatment discontinuation in CML patients in at least MMR when stopping. The TIGER study (NCT01657604) is currently investigating de-escalating maintenance therapy using low dose IFN as an inducer of immune surveillance following nilotinib discontinuation.


	
Upregulation of the immune checkpoint receptor PD-L1 and its receptors, PD-1 and B7.1, has been demonstrated in peripheral blood mononuclear cells from patients with CML. During the past 5 years, immune checkpoint inhibitors have revolutionized the management and treatment of cancer, because they have been associated with striking improvements in clinical outcomes in patients with some tumor types.
 
Programmed death ligand 1 (PD-L1) is an immune-checkpoint protein expressed on tumor cells and tumor-infiltrating immune cells that downregulates antitumoral T-cell function through binding to programmed death 1 (PD-1) and B7.1 (also known as CD80) receptors. The engineered, humanized IgG1 monoclonal anti-PD-L1 antibody atezolizumab blocks PD-L1-PD-1 and PD-L1-B7.1 interactions, resulting in restoration of antitumor T-cell activity and enhanced T-cell priming. Blocking PD-L1-B7.1 binding on T cells and antigen-presenting cells might additionally inhibit downregulation of immune responses, thus preventing inhibition of T-cell activation and cytokine production. Direct targeting of PD-L1 leaves the PD-L2-PD-1 interaction intact, potentially avoiding effects on immune homoeostasis. Atezolizumab is engineered to eliminate binding to Fc receptors and prevent Fc-effector function. This modification eliminates antibody-dependent cell mediated cytotoxicity and thus avoids potential loss of PD-L1-expressing T-effector cells and reduced anticancer immunity.
 
The combination of bosutinib plus atezolizumab in first line treatment in newly diagnosis chronic-phase CML patients would increase molecular responses and therefore TFR probabilities in these patients.
 
We propose an Open-Label Phase Ib/II Study of Bosutinib in Combination with Atezolizumab for the Treatment of New Diagnosis Chronic Phase-Chronic Myeloid Leukemia Patients.

Study Objectives	
Primary endpoint: Safety profile of bosutinib 400 mg daily in combination with atezolizumab in participants with chronic myeloid leukemia as first line treatments
 
Secondary endpoints:
 
• To evaluate the Major Molecular Response (MMR) and Molecular Response (MR) rates at 3, 6, 12 months and at the End of Treatment (EoT) visit.• Percentage of Participants Alive at Month 6, 12 and the EoT visit.• Number of confirmed MR4 and MR4.5 at end of treatment.• The rate of confirmed MR4 and MR4.5 at the end of treatment.• Number of Complete Cytogenetic Responses (CCyR) [Time Frame: At 1 year]• The rate of Complete Cytogenetic Response (CCyR) at 1 year.• Number of days to response (CCyR, MMR, MR4, MR4.5) [Time Frame: at the EoT visit]• The median time to response and the overall estimated probability of response (CCyR, MMR, MR4, MR4.5).• Number of overall surviving patients [Time Frame: at the EoT visit]• Number of progression-free survival patients [Time Frame: at the EoT visit]• Number of failure-free survival patients [Time Frame at the EoT visit]• Number of event-free survival patients [Time Frame: at the EoT visit]• Immunological Studies
Study Design	
This is a phase Ib/II, simple arm, open-label and dose-escalation study designed to determine the safety profile and the recommended phase III dose (RP3D) of bosutinib when administered in combination with atezolizumab in naïve patients with chronic myeloid leukemia in chronic phase.
 
The patients will be divided in two groups, with different start points, and will have three different therapy combinations during the study, which are described below. The first 10 patients included in the study will begin first. If at least 9 of these patients do not suffer DLTs during the first 2 cycles of the combined treatment (bosutinib 400 mg/day plus atezolizumab 840 mg every two weeks), the following 26 patients will be included, otherwise, the study will be terminated.

	
– First therapy
 
All patients included, both the first 10 patients and the next 26 patients, will receive bosutinib 400 mg/day in monotherapy for one cycle. All patients who tolerate this cycle of bosutinib treatment will continue to the second therapy (bosutinib plus atezolizumab).
 
– Second Therapy
 
*Group 1: The first 10 patients included
 
Only for the first ten patients included in the study, atezolizumab will be introduced at a dose of 840 mg every two weeks combined with 400 mg/day of bosutinib for 2 cycles (8 weeks). These patients will be closely monitored for safety issues.
 
If dose-limiting toxicities (DLTs) appear in 2 or more patients the study will end. If no relevant safety issues regarding the combination of drugs is detected the study will continue.
 
These initial 10 patients will cross-over from bosutinib 400 mg/day plus atezolizumab 840 mg every 2 weeks to bosutinib 400 mg/day plus atezolizumab 1680 mg every 4 weeks for 10 cycles (40 weeks).
 
*Group 2: The next 26 patients included
 
After receiving bosutinib 400 mg/day in monotherapy for one cycle (1st therapy), the last 26 patients included will receive bosutinib 400 mg/day plus atezolizumab 1680 mg every 4 weeks for 12 cycles.
 
Patients will be closely monitoring. If DLTs appear in 2 or more patients at a dose of 1680 mg of Atezolizumab every 4 weeks, the dose of atezolizumab will be reduced for all patients to an 840 mg Atezolizumab every 2 weeks dose.
 
All patients completing 12 treatment cycles (48 weeks) will begin the last therapy of study.
 
– Third Therapy
 
All patients completing cycle 12 with the combined bosutinib plus atezolizumab therapy will continue with bosutinib 400 mg/day in monotherapy for 12 more cycles.
 
A DLT would include either of the following adverse events occurring during of the bosutinib/atezolizumab therapy and that is considered at least possibly related to bosutinib and/or atezolizumab:
 
• Grade 4 neutropenia (<500/μl) persisting for >7 day duration or Grade 4 white cell count decrease for >7 day duration (<1000/μl).• Febrile neutropenia (ANC<1000/μl and fever \geq38.5°C).• Grade 4 thrombocytopenia >48 hour duration or with bleeding requiring platelet transfusion.• Any Grade 3 or 4 clinically evident non-hematological toxicity• Any \geqGrade 3 toxicity that requires >14 days to resolve (to \leqGrade 1 despite optimal medical therapy). 
DTLs will be graded according to the NCI CTCAE, v5.0.

Diagnosis and Main Inclusion Criteria	
Patients must fulfill the following criteria to be eligible for the study:
 
1. Male or female patient \geq 18 years of age.2. Evidence of a personally signed and dated informed consent document indicating that the patient (or a legal representative) has been informed of all pertinent aspects of the study.3. Patients who are willing and able to comply with scheduled visits, treatment plan, laboratory tests, and other study procedures

	
4. Newly Patient with Philadelphia chromosome positive chronic phase CML and BCR-ABL1 transcript detected at diagnosis.5. ECOG Performance Status of 0, 1, or 2.6. Adequate hepatic, renal and pancreatic function defined as:
a. Total bilirubin within normal range or Direct bilirubin $\leq 1.5 \times$ ULN,b. Aspartate aminotransferase (AST)/Alanine aminotransferase (ALT) $\leq 2.5 \times$ upper limit of normal (ULN) or $\leq 5 \times$ ULN if attributable to liver involvement of leukemia,7. Women of childbearing potential must have a negative pregnancy test documented prior enrollment. Women of childbearing potential and men must be using an adequate method of contraception.
Exclusion Criteria	
Patients eligible for inclusion in the study must not fulfill the following exclusion criteria:
 
1. Pregnant or lactating women,2. Participation in another clinical trial with any investigational drug within 30 days prior to study enrollment,3. Any prior medical treatment for CML, including tyrosine kinase inhibitors (TKIs), with the exception of hydroxyurea,4. Period of time since CML diagnosis longer than 6 months,5. Hypersensitivity to the active substances or to any of the excipients of the bosutinib and/or atezolizumab formulations,6. Major surgery or radiotherapy within 14 days of enrollment,7. Known clinically significant liver disease, including active viral, alcoholic, or other hepatitis, cirrhosis, and inherited liver disease,8. Concomitant use of or need for medications known to prolong the QTc interval,9. Concomitant use with strong CYP3A inhibitors (ketoconazole, itraconazole, clarithromycin), moderate CYP3A inhibitors (erythromycin, fluconazole, diltiazem), or strong CYP3A inducers (rifampin, carbamazepine, phenytoin),10. History of clinically significant or uncontrolled cardiac disease, including:
a. Stage II to IV congestive heart failure (CHF) as determined by the New York Heart Association (NYHA) classification system for heart failure.b. Myocardial infarction within the previous 6 months,c. Symptomatic cardiac arrhythmia requiring treatment,d. Diagnosed or suspected congenital or acquired prolonged QT history or prolonged QTc. (QTcF should not exceed 500 msec),11. Grade III or IV fluid retention,12. Uncontrolled hypomagnesemia or uncorrected symptomatic hypokalemia, due to potential effects on the QTc interval,13. Uncontrolled or symptomatic hypercalcemia,14. Recent or ongoing clinically significant gastrointestinal (GI) disorder e.g. Crohn's Disease, Ulcerative Colitis or prior total or partial gastrectomy,15. Autoimmune or infectious active disease that require treatment,16. CML patient not in chronic phase at diagnosis,17. Patients with known atypical transcript. An atypical transcript is defined by the presence of any transcript in the absence of the major transcripts b3a2 (e14a2) and b2a2 (e13a2) or p210 protein,18. Patients with known resistant mutation(s) (T315I, E255K/V, Y253H, F359C/V). It is not necessary to perform mutation tests on the patient to be included in the study if they were not previously performed,19. Individuals with an active malignancy,20. Known seropositivity to human immunodeficiency virus (HIV), current acute or chronic hepatitis B (hepatitis B surface-antigen positive) and/or hepatitis C.21. Any other disease, metabolic dysfunction, physical examination finding, or clinical laboratory finding that contraindicates the use of an investigational drug.22. Patients with severe renal impairment

Number of Patients	36 patients of both genders
Approximate Duration of Patient Participation	Approximately two years with treatment (25 cycles of 28 days).
Approximate Duration of Study	The estimated duration of the clinical trial is approximately 36 months, including 12 months for enrollment and 26 cycles of treatment/follow-up.
Approximate Number of Study Centers	Up to 10 centers; national (Spain).
Dosage Administration	
Group 1: The first 10 patients:
 
1. One cycle only with bosutinib 400 mg/day therapy.2. 2 cycles with bosutinib 400 mg/day plus atezolizumab 840 mg q2w therapy.3. 10 cycles with bosutinib 400 mg/day plus atezolizumab 1680 mg q4w therapy.4. 12 cycles with bosutinib 400 mg/day therapy. 
Group 2: The next 26 patients:
 
1. One cycle only with bosutinib 400 mg/day therapy.2. 12 cycles with bosutinib 400 mg/day plus atezolizumab 1680 mg q4w therapy.3. 12 cycles with bosutinib 400 mg/day therapy.
Efficacy Evaluation	Hematologic response rate, cytogenetic response rate, molecular response rate, and disease progression will be assessed according to standard criteria, as follows: 
• Bone marrow aspirates for assessment of cytogenetic response every 3 months after initiating bosutinib treatment. After complete cytogenetic response (CCyR) has been achieved, only if there is suspicion of disease progression,• BCR-ABL assessment to determine molecular response every 3 months after initiating bosutinib treatment,• Complete blood count (CBC) for assessment of hematologic response every 3 months,• Survival follow-up.
Safety Evaluation	Safety assessments will include physical and laboratory examinations. AEs will be graded according to the NCI CTCAE, v5.0. All patients receiving at least 1 dose of bosutinib will be considered evaluable for safety. The AE and VOE incidence rates, as well as the frequency of occurrence of overall toxicity -categorized by toxicity grades (severity). Listings of laboratory test results will also be generated, and descriptive statistics summarizing the changes clinically significant in laboratory tests over time will be presented.
Statistical Analysis	Statistical analysis and number of patients planned: There will be no formal calculation of the sample size for the study. The sample size is selected to allow sufficient data collection for the DLT and safety assessment. The minimum number of patients for the DLT evaluation will be 10 if no DLT is observed. After MTD is calculated, 26 more patients will be recruited for the dose escalation phase. 36 patients (both, a first group of 10 patients and a second of 26 patients) will receive bosutinib 400 mg/day in monotherapy during one cycle of treatment. According to previous experience (Tim H Brümmendorf et al, 2015; Jorge E cortes. el al, 2018), we assume that, at most, 15% of the patients included will not enter the dose escalation phase after the first month of treatment with bosutinib, due to side effects. Consequently, a total of 30-31 patients will receive the combination of bosutinib plus atezolizumab. Data will be analyzed using descriptive statistics. Continuous variables will be summarized using the number of observations, mean, standard deviation (SD), coefficient of variation, median and range as appropriate. The categorical values will be summarized using the number of observations and percentage as appropriate.

	This plan is extensively detailed in “PLANNED STATISTICAL ANALYSIS” of the project.
Study timelines	The first patient first visit (PPFV) is planned for September 2020 and the recruitment period is planned to last 1 year. The data cutoff date will be the date of the last patient last visit (LPLV).
Rationale for Number of Patients	This is a single-arm exploratory study.

